### 7.2.3. Metabolic Laboratory Evaluations

Fasting status was recommended for postbaseline lipids, but not required for Screening lipid assessments. For metabolic assessments, including glucose and the lipid panel (ie, total cholesterol, triglycerides, LDL, HDL, total cholesterol to HDL ratio), only those measurements collected under fasting status will be summarized. P-values comparing the difference between the 2 treatment groups in baseline values and the change from baseline in metabolic assessment will be estimated from a 2-sided Wilcoxon rank sum test.

In addition, the number and percentage of subjects who took lipid modifying medications at study entry and initiated the medications during the study will be provided, respectively, for all subjects and subjects with both baseline and post-baseline fasting status. Statistical comparisons of the subject incidence rates between the 2 treatment groups will be performed using Fisher's exact test.

A lipid modifying medication is defined as a medication with WHO drug class (ATC drug class Level 2) "LIPID MODIFYING AGENTS" and CMDECOD containing the wording of "STATIN".

A sensitivity analysis of the fasting lipid tests will be performed by excluding subjects who took lipid modifying medications at study entry or initiated the medications during the study: baseline values, values at each visit, and changes from baseline at each visit will be summarized by treatment group using descriptive statistics. Baseline and change from baseline at each visit will be compared between the 2 treatment groups using a 2-sided Wilcoxon rank sum test.

Median (Q1, Q3) of change from baseline in fasting metabolic assessments over time will be plotted by treatment group.

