 - Lipid panels (total cholesterol, high-density lipoprotein [HDL], direct low-density lipoprotein [LDL], and triglycerides). It is recommended that participants fast for 8 hours prior to the blood draw.
 - HIV testing
 - HIV-1 Ab/Ag
 - HIV-1 RNA by polymerase chain reaction (PCR) for those participants who show symptoms consistent with acute infection and who have a negative fourth generation rapid HIV-1 Ab/Ag test or third generation rapid HIV-1 Ab test
 - Any participant with HIV-1 Ab/Ag or an HIV-1 infection (per [Appendix 7](#)) is a screen failure and will receive counseling and be referred for appropriate care
 - Hepatitis B testing (hepatitis B virus surface antigen [HBsAg], hepatitis B virus surface antibody [HBsAb], hepatitis B virus core antibody [HBcAb])
 - If a participant has a negative HBsAg, negative HBsAb, and positive HBcAb, HBV DNA testing will be completed. If the HBV DNA result is positive, the participant is a screen failure.
 - Participants found to be susceptible to HBV infection should be referred for HBV vaccination

— Hepatitis C testing

- If the HCV Ab result is positive, then HCV RNA will be completed unless there is documented evidence that sustained virologic response has been achieved. If the HCV RNA result is positive, the participant is a screen failure
- Computer-assisted self-interview (CASI) for: recent sexual risk events; interest in using PrEP; self-identification of transgender status; education and employment history; and use of tobacco and recreational drugs
- Risk reduction counseling including provision of condoms

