 - If the result for rapid testing is positive, a retest will be completed. If the retest is positive, an HIV-1 RNA by PCR test and sample collection for possible genotypic resistance testing will be completed.
- Urine collection for urinalysis, urine proteins, urine chemistry (uric acid, phosphate, and creatinine), and sample storage
- Blood sample collection for the following central laboratory analyses:
 - Hematology profile: CBC with differential and platelet count
 - Chemistry profile: alkaline phosphatase, AST, ALT, GGT, total bilirubin, direct and indirect bilirubin, total protein, albumin, LDH, bicarbonate, BUN, calcium, chloride, creatinine, glucose, phosphorus, magnesium, potassium, sodium, uric acid, and amylase (reflex lipase testing is performed in participants with total amylase $> 1.5 \times \text{ULN}$)
 - Estimated GFR according to the Cockcroft-Gault formula for creatinine clearance
 - Lipid panel (total cholesterol, HDL, direct LDL, and triglycerides). Participants should be instructed to fast (no food or drinks, except water, at least 8 hours prior to blood collection) (**every 24 weeks**)
 - HIV-1 Ab/Ag (not done for participants who acquire HIV)
 - If the HIV-1 Ab/Ag test is positive, an HIV-1 RNA by PCR test and sample collection for possible genotypic resistance testing will be completed as soon as possible.

- HIV-1 RNA by PCR test (see HIV Testing Algorithm, [Appendix 6](#)) and sample collection for possible genotypic resistance testing for any participants who:
 - 1) have a positive retest rapid HIV-1 Ab/Ag test (either fourth generation rapid HIV-1 Ab/Ag or third generation rapid HIV-1 Ab test)
 - 2) have a positive HIV-1 Ab/Ag test
 - 3) show symptoms consistent with acute infection regardless of the results of the rapid tests
 - 4) have a recent exposure that is considered high risk for HIV infection
 - 5) have been confirmed HIV-infected

For details regarding confirmation of HIV infection, please refer to Section [6.11](#).

— Hepatitis B testing (HBsAg, HBsAb, HBcAb) (**every 24 weeks**)

- If a participant has a negative HBsAg, negative HBsAb, and positive HBcAb, HBV DNA testing will be completed.
 - Participants who have tested positive for HBcAb on the study during a prior visit do not need to repeat the Hepatitis B testing panel during subsequent visits and instead will have HBV DNA testing performed at visits every 24 weeks

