#### 3.3. Strata and Covariates

This study does not use a stratified randomization schedule when enrolling subjects. Analyses of BMD, renal safety endpoints, weight and BMI will be adjusted for baseline F/TDF for PrEP.

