Last Dose Date (OLE phase) is defined as the latest of the OLE phase study drug end dates recorded on the "Extension Phase" Study Drug Administration eCRF with "Permanently Withdrawn" box checked for subjects who prematurely discontinued study drug according to the "Extension Phase" Study Drug Completion eCRF. This date will only be available for subjects treated in the OLE phase of the study. If the last dose date is missing for subjects who prematurely discontinued study drug in the OLE phase of the study, the latest of nonmissing OLE phase study drug start dates and end dates, the clinical visit dates, and the laboratory visit dates, excluding the date of 30-day follow-up visit, from the OLE phase data, will be used to impute the OLE phase last dose date.

**Last Study Date** is the latest of the randomized or OLE phase (if available) study drug start dates and end dates, the clinic visit dates, and the laboratory visit dates, including the 30-day follow-up visit date, for subjects who prematurely discontinued study or who completed study according to the Study Completion eCRF.

Last At-Risk of HIV Infection Date (DB phase) is (1) the date of HIV infection diagnosis as defined in Section 6.2.2 for subjects who have been diagnosed as infected with HIV during the DB phase or (2) the date of the last post-baseline HIV laboratory test (either local rapid or Covance HIV laboratory tests, including the 30-day follow-up visit date) during the DB phase for subjects who have not been infected with HIV during the DB phase.

Last At-Risk of HIV Infection Date (OLE phase) is (1) the date of HIV infection diagnosis as defined in Section 6.2.2 for subjects who have been diagnosed as infected with HIV during the OLE phase or (2) the date of the last post-baseline HIV laboratory test (either local rapid or Covance HIV laboratory tests, including the 30-day follow-up visit date) during the OLE phase for subjects who have not been infected with HIV.

**Baseline value** is defined as the last value obtained on or prior to Study Day 1 for each phase for all assessments, except for DXA BMD. The baseline value for DXA BMD is defined as the last value obtained on or prior to Study Day 14 of each phase.

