### 7.2.2.1. Treatment-Emergent Laboratory Abnormalities

Only the laboratory abnormalities during the randomize phase will be summarized. Treatment-emergent laboratory abnormalities are defined as values that increase at least 1 toxicity grade from baseline at any postbaseline time point, up to 30 days after permanent discontinuation of randomized study drug or the last available date for subjects who were still on study drug or on a study drug interruption during the DB phase at the time of analysis. If the relevant baseline laboratory value is missing, any abnormality of at least Grade 1 observed within the time frame specified above will be considered treatment-emergent.

Fasting glucose and nonfasting glucose (including glucose results without a known fasting status) are graded based on different grading scales as specified in the protocol. Fasting status was recommended for postbaseline lipids and not required for Screening lipid assessments. For nonfasting glucose (including glucose results without a known fasting status), fasting glucose, fasting total cholesterol, fasting triglycerides and fasting LDL, maximum postbaseline grade, instead of treatment-emergent grade, will be summarized, as fasting status at baseline was approximately half fasting and half nonfasting; therefore, whether an abnormality is treatment-emergent or not cannot be determined for approximately half of the subjects.

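### The treatment tests for fasting lipids and glucose use change from baseline, which about half of participants lack, and the overall test is not stratified by baseline F/TDF; precision is lost, without bias

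*SAP*

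**What the plan says.** **Which values enter.** For glucose and the lipid panel, SAP 7.2.3 states that "only those measurements collected under fasting status will be summarized". Between-arm p-values are planned for baseline values and for change: "the change from baseline in metabolic assessment will be estimated from a 2-sided Wilcoxon rank sum test". The sensitivity analysis without users of lipid-modifying drugs uses the same test.

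**Where baseline comes from.** SAP 3.8.1 defines baseline as "the last value obtained on or prior to Study Day 1 for each phase for all assessments, except for DXA BMD". The SAP Appendix 1 schedule shows lipids and chemistry at screening and neither on Day 1. Protocol 6.2.1 asks for fasting at screening only as advice: "It is recommended that participants fast for 8 hours prior to the blood draw". From Week 24, Protocol 6.3 has participants instructed to fast for the 24-weekly lipid draw, although SAP 7.2.3 calls postbaseline fasting recommended.

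**How many had a fasting baseline.** SAP 7.2.2.1 reports that "fasting status at baseline was approximately half fasting and half nonfasting". For that reason it drops treatment-emergent grading of these tests and summarises the maximum postbaseline grade. SAP 3.6.1 imputes nothing unless a method is specified, and none is given for lipids or glucose. In its lipid-medication summary, SAP 7.2.3 itself names a subset of "subjects with both baseline and post-baseline fasting status".

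**Adjustment for prior PrEP.** SAP 3.3 says "Analyses of BMD, renal safety endpoints, weight and BMI will be adjusted for baseline F/TDF for PrEP". Metabolic endpoints are not on that list. SAP 7.2.3.1 does run Wilcoxon tests on baseline and change within each baseline F/TDF subgroup.

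**The concern.** A change score needs a fasting value at both ends. About half of participants have no fasting baseline, so their fasting follow-up samples can appear in the descriptive tables but in no treatment p-value on lipids or glucose. With 5387 in the Safety Analysis Set (SAP Appendix 3), that is roughly 2,700 people.

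The loss is avoidable. Fasting at screening precedes randomisation, so the arms are comparable both among those with a fasting baseline and among those without one. SAP 7.2.2.1 works around the same gap for graded abnormalities; SAP 7.2.3 does not for the test.

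The overall test also differs from its siblings. Renal biomarkers use a Van Elteren test stratified by baseline F/TDF (SAP 7.4.1). Serum creatinine, weight and BMI use ANCOVA with baseline value and baseline F/TDF (SAP 7.4.4, 7.5).

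Comparing general safety is a stated secondary objective. In a safety comparison, an imprecise null result can look more reassuring than it is.

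**Working it through.** The documents give no power, SD or correlation for the metabolic tests, so there is no planned figure to reproduce.

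**Inputs**
- Share with a fasting baseline: f = 0.5 (SAP 7.2.2.1).
- Allocation 1:1, two-sided 5% (SAP 1.2, 3).
- rho, the correlation between fasting baseline and fasting follow-up: assumed 0.5 to 0.8, with 0.3 to 0.9 as a wider range.
- Also assumed: equal variance sigma² at both times, and follow-up fasting unrelated to screening fasting.

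**Formulas** (variance of an arm mean, in units of sigma²/n, where n per arm have a fasting follow-up value)
- Planned change score in half the sample: 2(1−rho)/0.5 = 4(1−rho).
- Baseline adjustment in the same half: 2(1−rho²).
- All fasting follow-up values, baseline-adjusted where a fasting baseline exists, strata combined by inverse variance: 2/[1/(1−rho²)+1] = 2(1−rho²)/(2−rho²).
- The same two strata weighted by size: (2−rho²)/2.

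| rho | Planned | All values, inverse variance | Reduction | Size-weighted | Change from plan |
|---|---|---|---|---|---|
| 0.3 | 2.80 | 0.953 | 66% | 0.955 | −66% |
| 0.5 | 2.00 | 0.857 | 57% | 0.875 | −56% |
| 0.6 | 1.60 | 0.780 | 51% | 0.820 | −49% |
| 0.7 | 1.20 | 0.675 | 44% | 0.755 | −37% |
| 0.8 | 0.80 | 0.529 | 34% | 0.680 | −15% |
| 0.9 | 0.40 | 0.319 | 20% | 0.595 | +49% |

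Simulation of the inverse-variance analysis (400 per arm, 3000 runs) gave reductions of 56.7%, 47.3% and 33.1% at rho 0.5, 0.65 and 0.8. The share f matters too: for rho 0.5 to 0.8 the reduction is 65% to 42% at f = 0.4 and 50% to 27% at f = 0.6.

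**Where the gain comes from.** Replacing the change score by baseline adjustment in the same half multiplies the variance by (1+rho)/2, a reduction of 25% at rho 0.5 and 10% at rho 0.8. Adding the omitted participants multiplies what remains by 1/(2−rho²), a further 43% and 26%. Check: 0.75 × 0.571 = 0.429, and 0.90 × 0.735 = 0.662.

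**Baseline F/TDF.** This is separate from the table. With a share p of users and a shift of d SDs of change, stratifying removes p(1−p)d²/[1+p(1−p)d²]. For assumed p of 0.1 to 0.5 and d of 0.2 to 0.5 that is 0.4% to 6%.

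**Can the existing code be reused?** The rank analysis of covariance in Appendix 12 item 18 sums over strata, in effect the size-weighted column. It breaks even with the plan where 2−rho² = 8(1−rho), that is rho = 4−√10 = 0.84, and loses above that. Simulation of that procedure with a fasting-baseline stratum added (1000 per arm) gave reductions of 55%, 48%, 37% and 13% at rho 0.5 to 0.8, and power falling from 79% to 60% at rho 0.9. Its regression step would also drop every row without a baseline, removing the same half again.

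**The case against.** The strongest reply is that little of practical weight is lost. Half of 5387 is about 1,347 per arm, which gives 80% power for 2.80 × √(2/1347) = 0.11 SD of change; with 30% more missing, 0.13 SD. The tests are outside the alpha-controlled family, and no clinically relevant difference that would be missed has been identified. This stands, and it limits the weight of the point.

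Second, a reader might infer that the data of half the participants are thrown away. They are not. SAP 7.2.1 summarises values at each postbaseline window without requiring a fasting baseline, and SAP 7.2.2.1 summarises maximum postbaseline grade. What is missing is a treatment comparison of those values.

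Third, a reader might infer that the SAP ignores prior F/TDF use for these endpoints. SAP 7.2.3.1 tests within the F/TDF subgroups. Only the overall test is unstratified.

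Fourth, participants who did not fast at screening may also fast less often later, and the size of the gain assumes that they do not. This also stands: the recoverable share could be smaller than calculated.

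Fifth, SAP section 1 says that the primary analysis had already been unblinded. A new test would come after that, so it has to be labelled and kept supplementary.

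**Conclusion.** The point holds as a loss of precision. The lipid and glucose p-values rest on change scores available for about half of participants, and the overall test lacks the F/TDF stratification used for comparable endpoints.

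Under the stated assumptions, an efficient analysis of all fasting follow-up values would have 57% to 34% lower variance for rho 0.5 to 0.8, and 66% to 20% for rho 0.3 to 0.9. The documents do not support reading any of these as a known property of the trial, because rho appears in neither. Nor does the whole gain come from the omitted participants: 25% to 10% comes from replacing change scores by baseline adjustment. None comes from F/TDF, whose own contribution is small.

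A reader might also suspect bias. The documents do not support that: fasting at screening was settled before randomisation, so the selected half is comparable between arms. These are normal-theory variances; in simulation the planned Wilcoxon test had 77% to 78% power where the corresponding test on means was set to 80%.

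**What to change.** 1. In SAP 7.2.3, replace the overall rank sum test by the Van Elteren test stratified by baseline F/TDF for PrEP. The code is in Appendix 12 item 11. This aligns the metabolic test with its siblings but recovers none of the omitted half.
2. Add a supplementary comparison at each visit of fasting postbaseline values in everyone with a fasting sample at that visit. Stratify by baseline F/TDF and by fasting baseline available (yes/no). Use the fasting baseline as covariate only in the stratum that has it, and combine strata by inverse residual variance. Label it as added after the primary-analysis unblinding.
3. Do not apply the item 18 code unchanged, for the two reasons shown above: dropped rows and size weighting.
4. Keep the change-from-baseline table.

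The cost is SAP wording, one stratum variable, a modest amount of new code for item 2, and one extra p-value column. No new data are needed.

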88	LIPID MODIFYING AGENTS	HYPERLIPIDEMIA	ATORVASTATIN CALCIUM	
89	LIPID MODIFYING AGENTS	HYPERLIPIDEMIA	COLESEVELAM HYDROCHLORIDE	

	Medication Class (WHOATC2)	Indication (CMINDC)	WHOGEN
90	LIPID MODIFYING AGENTS	HYPERLIPIDEMIA	EICOSAPENTAENOIC ACID ETHYL ESTER
91	LIPID MODIFYING AGENTS	HYPERLIPIDEMIA	EZETIMIBE
92	LIPID MODIFYING AGENTS	HYPERLIPIDEMIA	FENOFIBRATE
93	LIPID MODIFYING AGENTS	HYPERLIPIDEMIA	FENOFIBRIC ACID
94	LIPID MODIFYING AGENTS	HYPERLIPIDEMIA	FISH OIL
95	LIPID MODIFYING AGENTS	HYPERLIPIDEMIA	GEMFIBROZIL
96	LIPID MODIFYING AGENTS	HYPERLIPIDEMIA	LOVASTATIN
97	LIPID MODIFYING AGENTS	HYPERLIPIDEMIA	OMEGA-3-ACID ETHYL ESTER
98	LIPID MODIFYING AGENTS	HYPERLIPIDEMIA	PELAGO
99	LIPID MODIFYING AGENTS	HYPERLIPIDEMIA	PRAVASTATIN
100	LIPID MODIFYING AGENTS	HYPERLIPIDEMIA	PRAVASTATIN SODIUM
101	LIPID MODIFYING AGENTS	HYPERLIPIDEMIA	ROSUVASTATIN
102	LIPID MODIFYING AGENTS	HYPERLIPIDEMIA	ROSUVASTATIN CALCIUM
103	LIPID MODIFYING AGENTS	HYPERLIPIDEMIA	SIMVASTATIN
104	LIPID MODIFYING AGENTS	HYPERLIPIDEMIA PREVENTION	ROSUVASTATIN CALCIUM
105	LIPID MODIFYING AGENTS	HYPERLIPIDEMIA,	PRAVASTATIN
106	LIPID MODIFYING AGENTS	HYPERLIPIDEMIA, MIXED	ATORVASTATIN CALCIUM
107	LIPID MODIFYING AGENTS	HYPERLIPIDEMIA, MIXED	FENOFIBRATE
108	LIPID MODIFYING AGENTS	HYPERTENSION	ATORVASTATIN
109	LIPID MODIFYING AGENTS	HYPERTENSION	PRAVASTATIN
110	LIPID MODIFYING AGENTS	HYPERTRIGLYCERDEMIA	ATORVASTATIN
111	LIPID MODIFYING AGENTS	HYPERTRIGLYCERIDEMIA	ATORVASTATIN CALCIUM
112	LIPID MODIFYING AGENTS	HYPERTRIGLYCERIDEMIA	FENOFIBRATE
113	LIPID MODIFYING AGENTS	HYPERTRIGLYCERIDEMIA	FENOFIBRIC ACID
114	LIPID MODIFYING AGENTS	HYPERTRIGLYCERIDEMIA	FIBRATES
115	LIPID MODIFYING AGENTS	HYPERTRIGLYCERIDEMIA	FISH OIL
116	LIPID MODIFYING AGENTS	HYPERTRIGLYCERIDEMIA	OMEGA-3 TRIGLYCERIDES
117	LIPID MODIFYING AGENTS	HYPERTRIGLYCERIDEMIA	PRAVASTATIN
118	LIPID MODIFYING AGENTS	HYPERTRIGLYCERIDEMIA,H YPERCHOLESTEROLEMIA	ATORVASTATIN
119	LIPID MODIFYING AGENTS	HYPERTRIGLYERIDEMIA	GEMFIBROZIL

	Medication Class (WHOATC2)	Indication (CMINDC)	WHOGEN	
120	LIPID MODIFYING AGENTS	HYPERTRYGLYCERIDEMIA PRAVASTATIN		
121	LIPID MODIFYING AGENTS	INDICATION HYPERLIPIDEMIA	FENOFIBRATE	
122	LIPID MODIFYING AGENTS	IRRITABLE BOWEL SYNDROME	FISH OIL	
123	LIPID MODIFYING AGENTS	ISCHEMIC HEART DISEASE	ROSUVASTATIN CALCIUM	
124	LIPID MODIFYING AGENTS	LDL-CHOLESTEROL GRADE 3 ELEVATION	ROSUVASTATIN	
125	LIPID MODIFYING AGENTS	MIXED DYSLIPIDEMIA	FENOFIBRATE	

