## 30) Lipid modifying medication analyses:

- a) Lipid modifying medication is defined to be the concomitant medication with ATC2 CMCLAS term "LIPID MODIFYING AGENTS" and CMDECOD contains wording of "STATIN" in the ADCM dataset.
- b) Subjects who took lipid-modifying medications at study entry refer to the subjects who use of the lipid-modifying agents at study day 1 (ie, the first dose date). More specifically, subjects with "Lipid Modifying Agent Use at Study Entry" include those subjects in Safety Analysis Set with: 1) any selected CM record with the start date ≤ the first dose date, and 2) the end date of the selected CM record is ongoing or the end date of the selected CM record > the first dose date.
- c) Subjects who initiated lipid-modifying medications during the study include the subjects in the Safety Analysis Set who didn't take lipid-modifying medications at study entry and met the following criteria: 1) for subjects who permanently discontinued study drug with any selected CM record started after the first dose date and on and prior to the last dose date; 2) for subjects who are still on study drug with any selected CM records started after the first dose date.
- d) For lipid-modifying medications with the start date completely unknown, we assume the start date is on or before the first dose date, lipid-modifying medication was considered as being taken at study entry if the end date is not prior to the first dose date (ie, the end date is on or after the first dose date, completely unknown, or ongoing).
- e) Lipid modifying medications with the start date prior to the first dose date and the end date completely unknown were considered as being taken at study entry.
- 31) For figures, if at a visit where n (sample size) for any treatment group ≤ 5, data for that treatment group will not be displayed at the visit in figure (except the Kaplan-Meier figure), but all data will be included in the corresponding table summary.

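### The category labelled lipid modifying medications counts only statins, so users of fibrates, ezetimibe, nicotinic acid or colesevelam stay in the lipid sensitivity analysis and are missed in the comparison of use

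*SAP*

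**What the plan says.** SAP Section 7.2.3 compares the arms on fasting glucose and the lipid panel, listed as "total cholesterol, triglycerides, LDL, HDL, total cholesterol to HDL ratio". The main analysis restricts by fasting status only: "only those measurements collected under fasting status will be summarized". Nobody is left out for medication.

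The same section adds two supporting analyses that depend on a drug definition:

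- The number and percentage of participants on lipid modifying medications at entry, and of those starting them on study, compared between arms by Fisher's exact test.
- A sensitivity analysis of the fasting lipid tests, "excluding subjects who took lipid modifying medications at study entry or initiated the medications during the study", using Wilcoxon rank sum tests.

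The definition has two conditions that must both hold: membership of the ATC level 2 class, and "CMDECOD containing the wording of 'STATIN". Appendix 12 item 30(a) gives the same rule to the programmers: "CMDECOD contains wording of 'STATIN' in the ADCM dataset". For participants who permanently discontinued study drug, item 30(c) dates initiation by "any selected CM record started after the first dose date and on and prior to the last dose date", which is after randomisation. Neither place explains the restriction to statins, and neither keeps values from before initiation.

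**The concern.** The label and the rule describe different things. The label covers drugs that modify lipids; the rule covers one group of them. If the SAP's own coded data hold other lipid-lowering drugs in the same class, two outputs fail to do what their titles say. The sensitivity analysis still contains treated participants, and the table of use and initiation is a statin table under a broader name.

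This matters most for triglycerides and HDL. On general pharmacological grounds (an assumption here, not a statement in the documents), these are the tests on which fibrates and nicotinic acid would be expected to act. A reader who sees the sensitivity analysis agree with the main analysis could take that as evidence that lipid-lowering treatment did not affect the comparison, when part of that treatment had been left in.

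The treatment of on-study starters is a separate, smaller matter. Removing the whole participant discards measurements that the new drug could not have influenced.

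**Working it through.** The plan gives no sample size, event count or effect size for the lipid analyses, so there is no stated figure to reproduce. The check applies the rule to the SAP's own medication list.

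**Input.** SAP Appendix 4, hyperlipidemia list. Rows 1 to 3 belong to other drug classes. Rows 4 to 155 are all in the class of lipid modifying agents: 155 − 3 = 152 rows. The list shows the generic name (WHOGEN), while the filter reads CMDECOD; I assume both carry the same drug name.

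**Captured by the rule (name contains STATIN).** Atorvastatin 41, rosuvastatin 23, pravastatin 18, simvastatin 8, lovastatin 3, pitavastatin 1: 94 rows, 94/152 = 62%.

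**Not captured.** 152 − 94 = 58 rows, 38%:

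- Fibrates: fenofibrate 13 + fenofibric acid 2 + gemfibrozil 5 + unspecified fibrates 1 = 21
- Ezetimibe: 3
- Nicotinic acid: 4
- "COLESEVELAM HYDROCHLORIDE": 1
- Fish oil, omega-3 and related products: 28
- One brand name whose content is not stated (PELAGO): 1

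The first four groups give 21 + 3 + 4 + 1 = 29 rows, 29/152 = 19%. Five of the 21 fibrate rows name raised triglycerides as the indication (rows 41, 112, 113, 114 and 119).

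**Internal contrast.** Under Appendix 4, a fenofibrate record for hypertriglyceridemia that starts by the first dose flags the participant as having a history of hyperlipidemia. Under Section 7.2.3 the same record counts as no lipid modifying medication.

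**Effect on the Fisher table.** Under item 30(c), a participant on fenofibrate at entry who later adds a statin is a new initiator. A participant who starts fenofibrate on study is not an initiator at all.

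**Starters.** Fasting lipids are windowed every 24 weeks (SAP Table 3-2). A participant who starts a statin at Week 60 loses the Week 24 and Week 48 values as well as the later ones. Censoring at initiation would keep Weeks 24 and 48. From Week 72 on, the two rules leave out the same person.

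**How far could dropping starters move an arm difference?** The documents give nothing to fix this, so the following is illustration only, with every input assumed: normally distributed LDL change with SD 25 mg/dL; true arm difference 3, 6 or 10 mg/dL; overall initiation 1%, 3% or 6%; log-odds of initiation per SD of rise 0, 0.5, 1 or 2; 400,000 simulated participants per arm.

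- Initiation unrelated to the rise: no change beyond simulation noise.
- Difference 6, initiation 3%, log-odds 1: mean difference 5.76, a shrinkage of 0.24/6 = 4%.
- Difference 10, initiation 6%, log-odds 2: 8.85, a shrinkage of 1.15/10 = 11.5%.
- Difference 3, initiation 6%, log-odds 2: 2.63, a shrinkage of 0.37/3 = 12%, the largest in the grid.

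The model leaves out the fall in lipids after a statin starts, so it does not settle the sign of the net effect.

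**The case against.** The strongest reply is that the definition is explicit and identical in both places, so no programmer is misled, and that little depends on it. Much of this stands. The main fasting-lipid comparison excludes nobody for medication. Maximum postbaseline grades for fasting cholesterol, triglycerides and LDL are also summarised without a medication exclusion (SAP Section 7.2.2.1). Section 7.6.5 tabulates concomitant non-ARV drugs by arm and preferred name, so fibrate, ezetimibe and niacin use will be visible, though without a test. Lipids are not among the named primary or secondary endpoints and carry no alpha.

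The row count also has limits. Rows are drug-by-indication text, and spelling variants inflate them: fenofibrate appears separately under three spellings of hypercholesterolemia. Anyone taking one of these drugs together with a statin is already excluded. The text filter also does something useful by keeping out the 28 fish-oil and omega-3 rows, so simply deleting the STATIN condition would be a poor repair.

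A reader might go further and infer that dropping starters removes the largest on-treatment rises, and that both features pull the arm difference toward zero. The documents do not support that. Some listed statin indications fit it, such as a grade 3 LDL elevation or worsening dyslipidemia. Others are stroke or coronary prevention, and a statin may be started for a high level rather than a large change. Excluding a starter also removes the fall after treatment begins, and a stable fibrate from before entry has no stated arm-specific effect on change from baseline.

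These points limit the importance of the matter. They do not make the rule match its label.

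**Conclusion.** The point holds as a mismatch between label and rule. As written, users of fibrates, ezetimibe, nicotinic acid or colesevelam who take no statin stay in the analysis intended to exclude lipid-modifying treatment, and the Fisher comparison misclassifies their use and initiation. The only size the documents allow is 29 of 152 listed rows; the number of participants, overall or per arm, is unknown.

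The loss of pre-initiation values is real but secondary. Any claim about the direction or size of bias would rest on assumptions outside the documents. No conclusion on efficacy or on an alpha-controlled endpoint is touched. This is a minor correction to a supportive analysis.

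**What to change.** In SAP Section 7.2.3 and Appendix 12 item 30(a), define the category as the ATC level 2 class of lipid modifying agents limited to statins, fibrates, ezetimibe, nicotinic acid and bile-acid sequestrants, with fish oil and omega-3 products left out by name. Resolve the one brand of unstated content before the filter is run. Use this definition for both the exclusion and the Fisher table, and show statins as a sub-row so that the present count is kept. If the sponsor wants statins only, the titles should at least say so.

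For participants who start such a drug on study, keep values up to the day before initiation and censor later ones. Item 30 has rules for completely unknown start dates and for unknown end dates but none for partial start dates, so one must be added. State that censoring recovers the earlier visits only: after initiation the same participants are missing, and selection on a post-randomisation event remains.

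The cost is a short text change and a revised programming filter on medication data that are already coded. The wider definition leaves slightly fewer participants in the sensitivity analysis.
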